7.4.2 Dose Adjustment Outside the DLT Assessment Window (Including Dose Expansion Part)

Table 7 Dose Adjustment for Hematologic Toxicity

CTCAE v5.0 Grade	Action
Grade 1 or 2	None
Grade 3 or 4 (believed to be related to HMPL-306 and NOT underlying disease)	
 • Hold drug. • If the toxicity improves to Grade ≤ 2 within 28 days, then resume at original dose. • If the toxicity recurs at original dose, then resume at 1 dose lower provided the toxicity improves to Grade ≤ 2 within 28 days. • If the toxicity recurs in setting of prior dose level reduction, then resume at the next lower dose provided the toxicity improves to Grade ≤ 2 within 28 days. • In the event the toxicity does not improve to Grade ≤ 2 within 28 days or toxicity recurs despite 2 dose reductions, HMPL-306 treatment is to be permanently discontinued.

AE = adverse event; CTCAE v5.0 = Common Terminology Criteria of Adverse Events version 5.0.

Table 8 Dose Adjustment for Non-Hematologic Toxicity

CTCAE v5.0 Grade	Action
Grade 1 or 2	None
Grade 3 ¹	
 • Hold drug. • If the toxicity improves to Grade ≤ 2 within 28 days then resume at original dose. • If the toxicity recurs at original dose, then resume at 1 dose lower provided the toxicity improves to Grade ≤ 2 within 28 days. • If the toxicity recurs in setting of prior dose level reduction, then resume at the next lower dose provided the toxicity improves to Grade ≤ 2 within 28 days. • In the event the toxicity does not improve to Grade ≤ 2 within 28 days or toxicity recurs despite 2 dose reductions, HMPL-306 treatment is to be permanently discontinued.
Grade 4 ¹	
 • Permanently discontinue treatment with HMPL-306.

CTCAE v5.0 = Common Terminology Criteria of Adverse Events version 5.0.

1. Dose adjustments or modifications for Grade ≥ 3 nausea, vomiting, diarrhea, constipation, fatigue, and electrolyte imbalance are not required if they can be controlled by systemic or local drug administration.

7.4.3 Dose Adjustment for QT Interval Prolongation

Table 9 Dose Adjustment for QT Interval Prolongation

Degree of QTcF Prolongation	Action
QTcF >480 ms to 500 ms	
 Hold drug. Monitor and supplement electrolyte levels as clinically indicated. Review and adjust concomitant medications with known QTcF interval-prolonging effects. Restart HMPL-306 at original dose if QTcF interval returns to ≤ 480 ms. Monitor ECGs at least weekly for 2 weeks following resolution of QTcF prolongation.
QTcF >500 ms	
 Hold drug. Monitor and supplement electrolyte levels as clinically indicated. Review and adjust concomitant medications with known QTcF interval-prolonging effects. Restart HMPL-306 at half of the original dose when QTcF interval returns to within 30 ms of baseline or ≤ 480 ms. Monitor ECGs at least weekly for 2 weeks following resolution of QTcF prolongation. Consider re-escalating HMPL-306 to the original dose if an alternative etiology for QTcF prolongation can be identified.
QTcF interval prolongation with signs/symptoms of life-threatening arrhythmia	
 Discontinue HMPL-306 permanently.

ECG = electrocardiogram; QT = interval from the start of the Q wave to the end of the T wave; QTcF = QT interval corrected for heart rate using Fridericia's formula.

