7.4 Dose Adjustments

7.4.1 Adjustment of Dose within the DLT Assessment Window

In the DLT assessment window, subjects without DLT must not undergo dose reduction of HMPL-306.

- If a DLT occurs, HMPL-306 administration will be suspended and appropriate supportive treatment will be given
- If a DLT returns to Grade 1 or lower within 14 days, HMPL-306 may be resumed at the previous lower dose if the investigator assesses that the subject may still benefit
- If a DLT has not returned to Grade 1 (inclusive) or lower within 14 days, or DLT reoccurs at the lowered dose, HMPL-306 will be terminated

- If the subject has an AE that does not meet the DLT criteria, the subject should continue HMPL-306 according to the original planned dose; for Grades 3 and 4 non-DLT AEs, HMPL-306 can be suspended as necessary as assessed by the investigator

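### Protocol Table 9, first row: restarting at the original dose has no exception for a subject already halved after QTcF above 500 ms, so a later reading of >480 to 500 ms that recovers returns that subject to full dose

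*Protocol*

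**What the plan says.** Protocol section 7.4.3, Table 9, has three rows.

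- **First row**, headed "QTcF >480 ms to 500 ms": hold drug, attend to electrolytes and concomitant medication, then "Restart HMPL-306 at original dose if QTcF interval returns to" 480 ms or less. No condition refers to the dose the subject is taking or to any earlier reduction.
- **Second row**, QTcF above 500 ms: "Restart HMPL-306 at half of the original dose when QTcF interval returns to within 30 ms of baseline", or to 480 ms or less. The way back to full dose is discretionary and conditional: "Consider re-escalating HMPL-306 to the original dose if an alternative etiology for QTcF prolongation can be identified".
- **Third row**, prolongation with signs or symptoms of life-threatening arrhythmia: permanent discontinuation.

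Tables 7 and 8 in section 7.4.2 deal with recurrence in two steps. For a first recurrence: "If the toxicity recurs at original dose, then resume at 1 dose lower". For a later one: "If the toxicity recurs in setting of prior dose level reduction, then resume at the next lower dose". Both steps require recovery to Grade 2 or lower within 28 days. Table 9 has no recurrence rule.

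Inside the DLT window, section 7.4.1 says that "subjects without DLT must not undergo dose reduction of HMPL-306". A subject with a DLT that recovers may resume at the previous lower dose.

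**The concern.** The second row protects a subject who has exceeded 500 ms: the dose is halved and stays halved unless another cause is found. The first row, taken literally, removes that protection when the same subject is prolonged again but less severely. Renewed evidence of a QT effect on half dose would then lead to more drug, with no alternative cause identified.

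This is a matter of subject safety. Protocol Table 3 describes QTcF prolongation as a class effect of approved IDH inhibitors and relies on the dose-modification guidance as part of the mitigation. No sample size, estimate or analysis rule depends on the point.

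**Working it through.** The plan states no figure to reproduce. The check is a comparison of the rules, followed by one ratio.

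**Step 1: what original dose means.** In the second row of Table 9 it is the dose that is halved and the dose to which a subject may be re-escalated, so it can only be the dose before reduction. Tables 7 and 8 give recurrence at the original dose and recurrence after a prior reduction as separate branches, so there too it excludes a reduced dose. Using the protocol's own vocabulary, a site would read the first row as an instruction to give full dose.

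**Step 2: follow one subject.** Let D be the original dose.

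| Event | Rule | Dose afterwards |
|---|---|---|
| Start | assigned dose | D |
| QTcF >500 ms, then recovery | Table 9, second row | 0.5D |
| QTcF >480 to 500 ms on 0.5D, then ≤480 ms | Table 9, first row | D |

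Ratio of restart dose to the dose held: D / 0.5D = 2.

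**Step 3: compare what could happen next to the same halved subject.**

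| What happens on 0.5D | Dose under the literal text | Ratio to 0.5D |
|---|---|---|
| No further prolongation, no alternative cause | 0.5D | 1 |
| >480 to 500 ms, recovers to ≤480 ms | D | 2 |
| >500 ms again, recovers | 0.5D (half of the original dose) | 1 |
| Prolongation with signs or symptoms of life-threatening arrhythmia | none (discontinued) | 0 |

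Only the second line produces an increase. The ordering is inconsistent: a moderate second event yields a higher dose than either no second event or a more severe one.

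**Step 4: look for another provision that sets the restart dose.**

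- Section 7.4.1 governs only the DLT window. It bars reduction in subjects without a DLT and sends those with a DLT to the previous lower dose, so the halving sequence belongs essentially after Cycle 1.
- Section 7.4.4 covers grade shifts from baseline, continuing unchanged when a toxicity is judged unlikely to become serious, the length of a delay, and simultaneous toxicities. None of these fixes a restart dose after a QT hold on a reduced dose.
- Section 6.2.1.1 provides for stopping treatment but does not set a restart dose.

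None of the three closes the gap.

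**The case against.** The strongest reply is that no investigator would read the table this way. The term is never formally defined. The second row is the specific rule for a subject who has exceeded 500 ms, and its alternative-cause condition can be read as still binding. Tables 7 and 8 show that the protocol expects a lower dose, not a higher one, when toxicity recurs after a reduction. The Amendment 1 history records that a provision for intra-subject dose escalation was removed from this same section. All of this stands as evidence of intent, and it is why the point is best described as a probable drafting slip. It does not change what the first row tells a site to do.

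Safeguards also exist. The first row requires a hold, recovery to 480 ms or less and a review of concomitant medication, followed by this step: "Monitor ECGs at least weekly for 2 weeks following resolution of QTcF prolongation". The investigator can stop treatment, and the Safety Review Committee monitors safety throughout. These reduce the risk, but none of them sets the restart dose.

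A reader might infer that any second prolongation on half dose doubles the dose. The documents do not support that: the second and third rows of Table 9 give half dose again or discontinuation. A reader might also infer that the problem arises during DLT assessment. Section 7.4.1 has its own rules there.

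The case is probably rare. It needs a reading above 500 ms, recovery, halving, a second reading in a 20 ms band, and recovery again. Protocol section 4.1.1 reports no DLTs or safety concerns at dose levels 1 to 4, although levels 5 to 8 are higher. That limits the expected number affected. It is no reason to leave the instruction as it is.

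**Conclusion.** The point holds in this limited form. For a subject already halved under the second row of Table 9, the first row literally directs a return to full dose after a reading of >480 to 500 ms that recovers. The increase is two-fold and bypasses the alternative-cause condition.

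The conclusion rests on reading original dose as the dose before reduction, which is how the protocol uses it elsewhere. It applies to the Amendment 2 text and essentially after the 28-day DLT window. It does not show that the sponsor meant to re-escalate such subjects, or that any subject was in fact re-escalated.

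The frequency is not given and is likely low. According to the SAP introduction only the escalation part was enrolled, and SAP section 2.3.1 estimates 27 to 36 subjects. The change should still be made, because the stated rule gives a less safe dose and correcting it costs very little.

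**What to change.** In the first row of Table 9, replace the instruction to restart at the original dose with one to restart at the dose being taken when drug was held. For the subject followed above, the restart is then 0.5D, a ratio of 0.5D / 0.5D = 1. Return to the original dose after a QT-related halving would follow only the second row's alternative-cause condition. The same wording covers a subject reduced earlier for another toxicity under section 7.4.1 or Tables 7 and 8. Whether to step down further on recurrence, as Tables 7 and 8 do, is for the sponsor to decide.

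The cost is one phrase in one table and a memo to sites, with no new data or procedures. Nothing changes for a subject who has not been reduced. The downside is that some halved subjects will stay at lower exposure than the literal text would give them.

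The SAP is based on protocol Amendment 3, which was not supplied, so first check whether that amendment already changed Table 9. If treatment has ended, carry the wording into later protocols that reuse the table.

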7.4.4 General Dose Adjustment Note

The severity of DLTs/AEs will be graded according to the National Cancer Institute Common Terminology Criteria for Adverse Events (NCI CTCAE) Version 5.0. Reasons for dose modifications or delays, the supportive measures taken, and the outcome should be documented in the subject's chart and recorded in the eCRF.

- For any concomitant conditions already apparent at baseline, the dose modifications will apply according to the corresponding shift in toxicity grade, if the investigator feels it is appropriate. For example, if a subject has Grade 1 asthenia at baseline that increases to Grade 2 during treatment, this will be considered a shift of 1 grade and will be treated as Grade 1 toxicity for dose modification purposes
- For toxicities that are considered by the investigator to be unlikely to develop into serious or life-threatening events, treatment can be continued at the same dose
- To recover from acute toxicity, unless otherwise indicated, the treatment can be delayed for up to 14 days. If a treatment delay longer than 14 days is required, treatment should be

discontinued. Continuation/resumption of treatment after an interruption of more than 14 days must be discussed with the medical monitor or his or her designee

- Where several toxicities with different grades or severity occur at the same time, the dose modifications should be according to the highest grade observed

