Abnormal hepatic function	In the HMPL-306 high-dose (CC mg/kg/day) group in rats, the CCI showed a CCI% increase and CCI showed CCI% increase. In clinical trials of both enasidenib and ivosidenib, AEs of abnormal hepatic function occurred, including elevated liver enzymes and elevated bilirubin.	Liver function will be routinely monitored.
Eye disorders	A total of 3 rats in the medium-dose (CC mg/kg/day) and high-dose (CC mg/kg/day) groups were found to have CCI. Considering that it is a vital functional organ, ophthalmological examination will be added to the clinical trials.	Ophthalmologic examinations will be performed during the Screening. If the subject has undergone the relevant examinations 60 days before treatment, they will not be required to repeat the test for Screening. After the start of treatment, ocular appearance, and slit lamp examinations will be performed every 3 cycles (ie, Day 1 of Cycles 4, 7, and 10) and during the end of treatment visit. Other ophthalmic examinations will be performed when clinically indicated.
Male reproductive system lesions	In rats given a medium-dose of HMPL-306 (CC mg/kg/day), CCI. In the high-dose (CC mg/kg/day) group, CCI.	Male subjects of childbearing potential will be included only if they agree to use effective contraception methods during the study and within 180 days after the last administration of the study drug.
Pancreatic lesions	CCI was observed in male rats administered with a high-dose of HMPL-306 (CC mg/kg/day) and was not observed during the recovery period.	Serum lipase and amylase will be monitored.
QTcF Interval Prolongation	The inhibitory rate of the negative reference standard and positive reference standard to the hERG potassium current of HMPL-306	QTcF will be monitored throughout the study, and dose modification guidelines are presented for associated AEs based on CTCAE grading criteria.

Table 3 Summary of Potential Risks of HMPL-306

Potential Risk of Clinical Significance	Summary of Data/Rationale for Risk	Mitigation Strategy
	
was within acceptable range (IC_{50} was as high as CCI μM).
 
CCI, QTcF interval prolongation has been seen as a class effect with other approved IDH inhibitors and may be seen with HMPL-306.
	

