8.1.2 Serious Adverse Event

An AE is considered “serious” if, in the view of either the investigator or the Sponsor, it results in any of the following outcomes:

- Death
- A life-threatening AE. An event is considered “life threatening” if, in the view of the investigator, its occurrence places the subject at immediate risk of death. It does not include an AE or suspected adverse reaction that, had it occurred in a more severe form, might have caused death
- Inpatient hospitalization or prolongation of existing hospitalization
- A persistent or significant incapacity or substantial disruption of the ability to conduct normal life functions
- A congenital anomaly/birth defect
- Important medical events that may not result in death, be life-threatening, or require hospitalization may be considered serious when, based on appropriate medical judgment, they may jeopardize the subject and may require medical or surgical intervention to prevent one of the outcomes listed in this definition. Examples of such medical events include allergic bronchospasm requiring intensive treatment in an emergency room or at home, blood dyscrasias or convulsions that do not result in inpatient hospitalization, or the development of drug dependency or drug abuse
- Signs, symptoms, or the clinical sequelae of a suspected overdose of either study drug or a concomitant medication. Overdose per se will not be reported as an AE/serious adverse event (SAE) unless it is an intentional overdose taken with possible suicidal/self-harming intent. Such overdoses should be reported regardless of sequelae

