8.5 Assessment of Severity

Investigators will seek information on AEs and SAEs at each subject contact. All AEs and SAEs, whether reported by the subject or noted by authorized study personnel, will be recorded in the subject's medical record and on the appropriate AE/SAE form.

For each AE and SAE recorded on the applicable eCRF, the investigator will make an assessment of severity through clinical description by referring to the 5-grade determination standard in the NCI CTCAE Version 5.0. Please use the guideline below for the assessment of severity when the observed or reported AE is not listed in the NCI CTCAE Version 5.0:

- Grade 1: Mild; asymptomatic or mild symptoms; clinical or diagnostic observations only; intervention not indicated
- Grade 2: Moderate; minimal, local, or noninvasive intervention indicated; limiting age-appropriate instrumental activities of daily living (ADLs). (Note: Instrumental ADLs

refer to preparing meals, shopping for groceries or clothes, using the telephone, managing money, etc.)

- Grade 3: Severe or medically significant but not immediately life threatening; hospitalization or prolongation of hospitalization indicated; disabling; limiting self-care ADLs (Note: Self-care ADLs refer to bathing, dressing and undressing, feeding self, using the toilet, taking medications, and not bedridden).
- Grade 4: Life-threatening consequences; urgent intervention indicated
- Grade 5: Death related to AE

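### Outside the DLT window, the same-dose bullet in Protocol 7.4.4 contradicts the hold instructions in Tables 7 and 8, and nothing says which prevails

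*Protocol*

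**What the plan says.** Protocol Section 7.4.2 governs dosing outside the DLT window. Both of its tables ask for no action at Grade 1 or 2.

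- Table 7 (hematologic) requires a hold at Grade 3 or 4, for events "believed to be related to HMPL-306 and NOT underlying disease". If the toxicity recovers to Grade 2 or lower "within 28 days, then resume at original dose". Recurrence leads to a lower dose. Failure to recover in that time, or recurrence after two reductions, leads to permanent discontinuation.
- Table 8 (non-hematologic) sets the same course at Grade 3, with no causality condition, and permanent discontinuation at Grade 4. Its one written exception is footnote 1: adjustments for Grade 3 or higher "nausea, vomiting, diarrhea, constipation, fatigue, and electrolyte imbalance are not required if they can be controlled by systemic or local drug administration".

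Section 7.4.4 is a general note that follows the tables. Its second bullet says that, for toxicities "considered by the investigator to be unlikely to develop into serious or life-threatening events, treatment can be continued at the same dose". It names no grade, no causality condition and no table.

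Inside the DLT window a different rule applies. Section 7.4.1 says that "for Grades 3 and 4 non-DLT AEs, HMPL-306 can be suspended as necessary as assessed by the investigator".

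**The concern.** A hold and permission to carry on at full dose cannot both apply to the same event. If the bullet is read as an exception to the tables, a site may dose through a Grade 3 event that Table 8 says to hold, without recording a deviation. If the tables are read as controlling, another site holds the drug for the same event. On recurrence the disagreement extends to dose reduction.

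What is at stake is subject safety and uniform handling across sites. Appendix 12 records that Tables 7 and 8 were added at a regulator's request, so the hold is the intended safety default. There is a smaller effect on reporting: Protocol 9.2.4 and SAP 5.2.11.2 summarize adverse events leading to interruption and reduction, and those counts would partly reflect which rule a site followed. The summaries are descriptive only.

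**Working it through.** No arithmetic applies. The check sets the two rules side by side for each kind of event after Day 28 of Cycle 1.

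| Event | Tables 7 and 8 | 7.4.4 bullet | Conflict? |
|---|---|---|---|
| Grade 1 or 2 | No action | May continue | No |
| One of the six footnote 1 toxicities, controlled | Adjustment waived | May continue | No |
| Other Grade 3 non-hematologic, judged unlikely to become serious | Hold | May continue | Yes |
| Grade 3 or 4 hematologic, thought related, judged unlikely to become serious | Hold | May continue | Yes |
| Grade 3 or 4 hematologic, not thought related | No row | May continue | No |
| Any event judged likely to become serious or life-threatening | Table action | Does not apply | No |

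Two rows conflict. The next step is to look for text that settles them.

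1. **A statement of precedence.** Neither 7.4.2 nor 7.4.4 has one.
2. **Deferring words.** The next bullet in 7.4.4, on treatment delay, gives way where other instructions exist. The same-dose bullet has no such words.
3. **Section 6.2.1.1, item 3.** It points to 7.4.2 as mandatory for withdrawal of treatment. That settles the Table 8 Grade 4 stop but not hold versus continue.
4. **Section 7.4.1.** Where the protocol means to give discretion at Grade 3 or 4, it says so by grade, and only inside the DLT window.

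The width of the two conflicting rows depends on how many Grade 3 events can pass the bullet's own test. Section 8.5 describes Grade 3, for events not listed in CTCAE, as "Severe or medically significant but not immediately life threatening; hospitalization or prolongation of hospitalization indicated". Section 8.1.2 counts "Inpatient hospitalization or prolongation of existing hospitalization" as a seriousness criterion. Many Grade 3 events therefore fail the test. The rest are Grade 3 events that an investigator expects to stay non-serious.

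An isolated Grade 3 liver-enzyme rise could be one. Protocol Table 3 notes that with two drugs of the same class "AEs of abnormal hepatic function occurred, including elevated liver enzymes and elevated bilirubin". Abnormal hepatic function is the only event of special interest listed in SAP 5.2.11.2. Protocol Section 7 has no separate hepatic dose rule, so Table 8 is the rule that the bullet would displace.

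**The case against.** The best reply is that a specific instruction normally prevails over a general permission. Section 7.4.4 is headed as a general note, its wording is permissive, and the tables are graded actions. Nor is the bullet idle on that reading. It covers Grade 3 or 4 hematologic events not thought related, for which Table 7 has no row, and inside the DLT window it agrees with 7.4.1 for non-DLT events. This is fair. It shows how a careful site would probably resolve the matter, and it rules out any claim that the bullet's only effect is to override the hold. But it remains an inference. The text gives no ranking, and a site that follows the bullet as written does what the protocol allows.

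The liver example can also be challenged. An investigator who knows the class risk may decline to judge such a rise unlikely to become serious. That is so; the example shows where the conflict can arise, not how often.

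A reader might infer two stronger things.

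- **That dose finding is compromised.** The documents do not support this. DLTs are counted in the 28-day window, where 7.4.1 governs dosing, so DLT-based MTD decisions do not depend on the bullet.
- **That the conflict is likely to arise in practice.** No rate of non-serious Grade 3 events outside footnote 1 is given. The 10%, 5% and 1% rates in Protocol 9.1.2.2 illustrate the chance of seeing a given adverse event among 95 expansion subjects and cannot be borrowed here. The one relevant clinical observation, in Protocol 4.1.1, is that dose levels 1 to 4 showed no DLTs or safety concerns.

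**Conclusion.** The point holds in limited form: the dosing rule is internally contradictory, and so wrong as written, for the two conflicting rows. This rests on the text alone and on the fact that no precedence is stated.

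The reach is Part 1 subjects who dose beyond Cycle 1. Protocol 9.1.2.1 plans 27 to 36 subjects for Part 1 as a whole. Enrollment at levels 1 to 4 was already complete when Amendment 2 was written, so a wording change reaches fewer. SAP Section 1 states that Part 2 enrolled nobody. No probability or expected count should be attached.

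A reader might also infer that the Table 8 Grade 4 stop is open to the bullet, or that the baseline-shift rule in 7.4.4 must be overridden. Neither follows. Section 6.2.1.1 already makes discontinuation under 7.4.2 mandatory. The baseline-shift rule is a separate, deliberate provision for conditions present at baseline.

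One reservation: the protocol supplied is Amendment 2, while the SAP is based on Amendment 3, which was not available. The wording may have changed.

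**What to change.** After checking Amendment 3, add one clause to the same-dose bullet in 7.4.4: *unless Tables 7 to 9 require a hold, dose reduction or discontinuation; leukocytosis is managed under Section 7.5.1; within the DLT window Section 7.4.1 applies*. Naming Table 9 keeps QTcF prolongation under its own rule. Naming 7.5.1 keeps its sequence for leukocytosis, which treats first and suspends drug only if that fails.

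Two further changes should not be made.

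- **An exception in Table 8 for unrelated events.** Without a grade cap it would loosen the Grade 4 discontinuation, which now applies whatever the cause.
- **An override of the baseline-shift rule for related events.** Grades 1 and 2 need no action, so under Tables 7 and 8 the rule matters only at observed Grade 3 or above. The override would leave it nothing to do for those events.

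The cost is lost discretion to dose through a non-serious Grade 3 event. A first event means a temporary hold, with the original dose resumed on recovery to Grade 2 or lower within 28 days. Recurrence leads to reduction, and non-recovery in that time to discontinuation. No visits or procedures are added.
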